3.3 Conditional Marginal Effects and Propensity Score Matching

- Conditional Marginal Effects:
 - For each HT risk level, conditional marginal effects will be estimated to quantify the Cerebrolysin effect on the likelihood of symptomatic HT and achieving FFO.

• Propensity Score Matching:

- Propensity scores will be calculated for each patient based on baseline covariates, such as age, NIHSS, and comorbidities, to balance baseline differences between treated and untreated patients.
- Treatment effects will be estimated for matched cohorts using:
 - Average Treatment Effect (ATE): Overall effect across the population.
 - Average Treatment Effect on the Treated (ATT) and Average Treatment Effect on the Untreated (ATC).

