The CEREHETIS trial is a prospective, randomized, open-label, multicenter, parallel-group, phase IIIb pilot study with an active control. Patients are randomized in a 1:2 ratio to receive either IVT alone or IVT with Cerebrolysin.

4. Sample Size Calculation

- **Primary Endpoint (HT Rate)**: Based on the assumption that 20% of control group patients will experience HT, with a target odds ratio (OR) of 0.5 in the Cerebrolysin group.
- Significance Level: 0.05
- **Power**: 80%
- Dropout Rate: 10%
- **Design:** 1:2 allocation ratio between the intervention and control groups to optimize power efficiency and minimize required sample size for this pilot study.

5. Randomization and Blinding

- **Randomization**: Simple randomization across centers using Bernoulli variates (probability parameter of 0.333), with sealed opaque envelopes for treatment allocation.
- **Blinding**: Due to the distinct yellow color of Cerebrolysin, treatment blinding was not feasible; however, imaging analyses are blinded.

6. Data Collection and Time Points

Data collection occurs at the following time points:

- Baseline (Day 0): Demographic data, NIHSS, CT, DTI baseline imaging
- Day 1: Follow-up imaging and NIHSS assessment
- Day 7 and Day 14: NIHSS score, follow-up CT, and DTI imaging on day 14
- Day 90: Modified Rankin Scale (mRS) assessment for functional outcome

7. Statistical Analysis

a. Descriptive Statistics

- **Continuous Variables**: Presented as median (M) and interquartile range (IQR) due to non-normal distributions.
- **Categorical Variables**: Presented as percentages and analyzed with χ^2 -tests.

b. Comparative Analysis

- Primary Analysis (HT Rates):
 - Comparison of HT Rates: Logistic regression will compare the rates of any and symptomatic HT between the Cerebrolysin and control groups. Odds ratios (OR) with 95% confidence intervals (CI) will be reported.
 - Adjustment for Confounders: Age, NIHSS, ASPECTS score, and baseline variables such as history of hypertension and previous stroke will be included in multivariate models to control for potential confounding.
- Secondary Analysis:
 - **Neurological Recovery (NIHSS)**: The Mann–Whitney U test will compare NIHSS scores between groups at day 1 and day 14.
 - **Functional Outcome (mRS)**: The mRS scores on day 90 will be assessed using a χ^2 -test for favorable outcomes (mRS ≤ 2). Additionally, a shift analysis will be conducted to evaluate distributional differences in mRS scores between groups.

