3.4 Heterogeneous Treatment Effect (HTE) Analysis with Matching-Smoothing

- Matching-Smoothing Method:
 - A matching-smoothing method will be applied to assess HTEs. This approach will use propensity scores to match patients and apply local polynomial smoothing to evaluate Cerebrolysin's impact across different HT risk levels.
- Kernel and Smoothing Parameters: The Epanechnikov kernel function will be used for smoothing. Bootstrapping (1,000 samples) will be performed to generate robust confidence intervals for the HTE estimates.
- **Output**: Local polynomial smoothed estimates of treatment effects across risk levels with 95% CIs, visually represented to show how Cerebrolysin's impact varies by HT risk level.

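### Propensity matching in Part II (3.3 and 3.4) removes no confounding in a randomised trial, can cost precision, and yields an ATT-ATC gap that is essentially noise

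*SAP*

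**What the plan says.** Part I, section 5 describes the assignment as "Simple randomization across centers using Bernoulli variates (probability parameter of 0.333", with sealed envelopes. The chance of receiving a given allocation is therefore a known constant and does not depend on any patient characteristic.

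Part II was added on 01 May 2023 as a post hoc analysis. Its section 3.3 computes a propensity score for each patient from covariates such as age, NIHSS and comorbidities, "to balance baseline differences between treated and untreated patients". Effects in the matched cohorts are to be given as the ATE and, separately, as "Average Treatment Effect on the Treated (ATT) and Average Treatment Effect on the Untreated (ATC". Section 3.4 uses the same device for the heterogeneity curves: "This approach will use propensity scores to match patients and apply local polynomial smoothing".

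Neither section fixes a matching ratio, a replacement rule, a caliper or the handling of unmatched patients.

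Part II also contains analyses that do not depend on matching: score-adjusted logistic models in 3.2, conditional marginal effects by risk level in 3.3, and Mantel-Haenszel subgroup estimates in 3.6.

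**The concern.** Propensity matching is a tool for studies in which treatment was chosen. Here it was randomised, so a baseline difference between the arms is chance. Chance imbalance can be worth adjusting for, but matching is a poor way to do it. It may discard patients, or lean on one partner per patient, where a regression model would use everyone.

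Splitting the effect into ATT and ATC presupposes that the patients who got the treatment differ systematically from those who did not. Randomisation removes that difference in expectation. In an analysis whose stated aim is to find heterogeneity, two separately reported effects that differ only by chance are easy to misread.

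At stake are the precision of the matched effects in 3.3 and of the curves in 3.4, and the clarity of what 3.3 reports.

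**Working it through.** **1. Why there is nothing to deconfound.** Let T be the randomised arm, Y1 and Y0 the two potential outcomes, and X the baseline covariates. Bernoulli assignment makes T independent of (Y1, Y0, X). Hence P(T=1 | X) is constant, and

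E[Y1−Y0 | T=1] = E[Y1−Y0 | T=0] = E[Y1−Y0],

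that is, ATT = ATC = ATE in expectation.

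**2. Inputs.** Part I, section 4 assumes "20% of control group patients will experience HT, with a target odds ratio (OR) of 0.5 in the Cerebrolysin group". The odds with Cerebrolysin are 0.5 × 0.20/0.80 = 0.125, so the risk is 0.125/1.125 = 11.1%.

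The SAP states no sample size, so there is no figure to reproduce. For scale only, the usual two-proportion formula (two-sided 0.05, 80% power, no continuity correction) gives 602 evaluable patients if Cerebrolysin is the smaller arm and 567 if control is. Both directions are needed because section 3 of Part I has "Patients are randomized in a 1:2 ratio to receive either IVT alone or IVT with Cerebrolysin" and section 4 has "1:2 allocation ratio between the intervention and control groups". That conflict is a separate matter and does not change the result here.

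**3. One-to-one matching without replacement, closed form.** Take 200 Cerebrolysin and 400 control patients and ignore covariates. Pairing leaves 200 and 200, so half of the larger arm is dropped.

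- Equal risks: (1/200 + 1/200)/(1/200 + 1/400) = 0.0100/0.0075 = 1.33 times the variance of the raw difference.
- Risks of 11.1% and 20% (binomial variances 0.0988 and 0.16): (0.0988/200 + 0.16/200)/(0.0988/200 + 0.16/400) = 0.001294/0.000894 = 1.45.

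**4. Simulation by randomised arm.** Each scenario had 1,000 trials with Bernoulli assignment, everyone analysed as assigned, a 20% control risk, and four independent normal covariates with assumed log-odds 0.3, 0.6, 0.2 and 0.2. Matching for ATE, ATT and ATC was to the single nearest neighbour on the estimated propensity, with replacement. For N = 600, P(Cerebrolysin) = 1/3 and OR 0.5:

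| Estimate | SD of risk difference | Variance relative to raw |
|---|---|---|
| Raw difference | 0.0312 | 1.00 |
| Standardised, covariate-adjusted | 0.0303 | 0.94 |
| Matched ATE | 0.0358 | 1.31 |
| Matched ATT | 0.0443 | 2.02 |
| Matched ATC | 0.0377 | 1.46 |

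Over all scenarios (N = 300 and 600; OR 0.5 and 1; and P(Cerebrolysin) = 2/3 with N = 600 and OR 0.5), the variance relative to the raw difference was:

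- matched ATE: 1.28 to 1.34
- ATT: 1.65 to 2.02
- ATC: 1.46 to 1.67
- one-to-one without replacement: 1.11 to 1.45
- standardisation: 0.91 to 0.96.

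The matched estimates were centred close to the truth throughout, to within simulation error. The damage is therefore variance, not bias. A variance ratio of 1.31 makes 600 patients worth about 600/1.31 = 458, and widens the interval by 0.0358/0.0312 = 1.15, or 15%.

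**5. The ATT-ATC gap.** At N = 600 and OR 0.5 the true within-sample gap has mean 0 and SD 0.003. The estimated gap has SD 0.038. It exceeds 5 percentage points in 19% of trials at N = 600 and 37% at N = 300. With OR 1, where both effects are exactly zero, the figures are 22% and 40%. Further simulations gave 35% at N = 300 and 20% at N = 600.

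**6. Sensitivity to the algorithm.** With four or more neighbours per patient the variance loss against the raw difference largely disappears. The figures in steps 3 to 5 therefore belong to single-neighbour or one-to-one matching, which the SAP permits but does not specify.

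**The case against.** The strongest defence has four parts.

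- **Simple randomisation can leave chance imbalance, so wanting balance is not an error.** This stands. It is an argument for covariate adjustment, which achieves the aim with less variance than single-neighbour matching.
- **The precision loss depends on an algorithm that the SAP does not name.** This also stands, and it limits the claim. With several neighbours there is little or no loss. But an unspecified ratio does not protect the analysis, since the costly variants remain open.
- **Matching is not all of Part II, and Part II is labelled post hoc with a warning about spurious associations.** True. The logistic models, the conditional marginal effects and the Mantel-Haenszel estimates stand without matching. What is affected is the matched effects in 3.3 and the curves in 3.4.
- **No section plans to test or interpret the difference between ATT and ATC.** Correct. A 5-point gap in the estimates is not a false-positive rate. The point is only that reporting both conveys no information that the ATE lacks.

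A reader might also infer something stronger from the words treated and untreated: that Part II regroups patients by what they received, so that non-receipt or crossover moves events between arms. The SAP does not support this. Those words are the ordinary vocabulary of propensity methods and can simply name the arms. No section mentions non-receipt, crossover or as-treated grouping. Section 3.5 of Part II speaks of treatment group, and section 3.2 of Part III of treatment arm. What can be said is that Part II does not define the term, and one sentence would settle it.

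**Conclusion.** The concern holds as a point about efficiency and clarity. With a known constant propensity, the matching in 3.3 and 3.4 removes no confounding. Under one-to-one or single-nearest-neighbour matching by arm, the estimates are unbiased but less precise: about 1.3 times the raw variance for the ATE and up to about 2 times for the ATT, against about 0.9 for covariate-adjusted standardisation. ATT and ATC are equal in expectation, so any gap between their estimates is essentially noise.

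The equality of ATT and ATC follows from the randomisation alone. The variance figures rest on assumed sample sizes of 300 and 600, assumed covariate strengths, the SAP's own 20% risk and OR of 0.5 (with OR 1 as the null case), and single-neighbour matching. They do not apply when several neighbours are used. The point does not touch the Part I primary analysis and does not imply that any Part II result is biased.

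**What to change.** In Part II, sections 3.3 and 3.4:

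1. State that treatment means the randomised arm, for all randomised patients.
2. Make standardised (g-computation) risk differences the main estimate, from a logistic model with arm and the same baseline covariates, listed in full.
3. In 3.4, smooth over the HT risk score using all randomised patients, either the outcome within each arm or the model-based patient-level differences. In the latter case include an arm-by-score term, so that the model does not impose the shape of the curve.
4. Drop ATT and ATC as separate estimands.
5. If matching is kept, label it a sensitivity analysis by randomised arm, and state the number of neighbours, the replacement rule, the caliper and what happens to unmatched patients.

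The cost is a few sentences in the SAP and simpler code. No new data are needed. If the matched results already exist, they can be shown beside the standardised ones.

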3.4 Heterogeneous Treatment Effect (HTE) Analysis with Matching-Smoothing

- Matching-Smoothing Method:
 - A matching-smoothing method will be applied to assess HTEs. This approach will use propensity scores to match patients and apply local polynomial smoothing to evaluate Cerebrolysin's impact across different HT risk levels.
- Kernel and Smoothing Parameters: The Epanechnikov kernel function will be used for smoothing. Bootstrapping (1,000 samples) will be performed to generate robust confidence intervals for the HTE estimates.
- **Output**: Local polynomial smoothed estimates of treatment effects across risk levels with 95% CIs, visually represented to show how Cerebrolysin's impact varies by HT risk level.

3.5 Generalized Ordered Logistic Regression

- Model Application:
 - Generalized ordered logistic regression with proportional and partial proportional odds assumptions will be applied to assess the association between mRS outcomes and HT risk.
 - **Brant Test**: The parallel odds assumption will be evaluated using the Brant test; if this assumption is violated, partial proportional odds models will be used.
 - **Output**: Estimated probabilities of mRS outcomes by HT risk and treatment group, with confidence intervals.

3.6 Meta-Analysis for Subgroup Heterogeneity

• Meta-analytic Techniques:

- Subgroups defined by HT risk scores (e.g., low, moderate, high HTI scores) will be treated as individual "studies" in a meta-analysis framework.
- Effect Size and Heterogeneity Assessment:
 - Fixed-effects Mantel–Haenszel models will assess binary outcomes, while random-effects models will evaluate heterogeneity using I² and H² statistics.
 - Small-study effects will be tested with the Egger test.
- Visualization: A forest plot will display effect sizes across subgroups.

4. Software and Statistical Significance

- Software: Stata v.14.2 and Stata v.17.0.
- **Significance Level**: α = 0.05 for all primary and secondary outcomes, with corrections for multiple comparisons using the Romano-Wolf adjustment.

5. Interpretation and Reporting

- Heterogeneity and Interpretation of HTEs:
 - Results will highlight subgroups where Cerebrolysin significantly reduces HT or improves functional outcomes. Any significant HTE findings will guide further investigation and inform potential stratification for future clinical recommendations.
- Limitations:
 - Post hoc analyses bear an inherent risk of finding spurious associations. To address this, all models and outcomes will be rigorously tested and reported regardless of significance. Additionally, findings will be discussed within the context of generalizability and the need for prespecified subgroup analyses in future trials.

This SAP for the post hoc analysis of the CEREHETIS trial outlines a robust, stratified approach to identify subgroups with potential benefits from Cerebrolysin. Advanced statistical methods for matching, smoothing, and meta-analysis will help address treatment heterogeneity, contributing valuable insights into personalized treatment strategies in ischemic stroke.

III. Statistical Analysis Plan for Secondary Data Analysis of the CEREHETIS Trial (Survival Analysis)

1. Introduction

This analysis aims to evaluate the timing of anticoagulation resumption in MCA stroke patients treated with Cerebrolysin, stratified by hemorrhagic transformation (HT) risk. The primary focus is on determining Cerebrolysin's effect on the incidence and hazard of HT over time and establishing the optimal timing for anticoagulation resumption using advanced survival and hazard-based methods. Patients will be categorized into low-risk (HTI = 0) and high-risk (HTI > 0) groups based on the Hemorrhagic Transformation Index (HTI) scores, and outcomes will be analyzed for both symptomatic and any HT within 14 days.

2. Objectives and Endpoints

- **Primary Objective**: To evaluate the effect of Cerebrolysin on the timing of safe anticoagulation resumption in stroke patients with varying HT risk levels.
- Primary Endpoints:
 - Incidence of **any HT** and **symptomatic HT** over 14 days.
 - **Timing of Anticoagulation Resumption**: Defined by inception points based on hazard deceleration (HD) curves.

• Secondary Endpoints:

- \circ Survival probabilities for HT stratified by HT risk groups (HTI = 0 vs. HTI > 0).
- Hazard and risk reduction metrics, including hazard ratios (HR), absolute risk reduction (ARR), number needed to treat (NNT), and restricted mean survival time (RMST) differences for symptomatic and any HT.

3. Statistical Analysis

3.1 Descriptive and Group Comparisons

- Descriptive Statistics:
 - Continuous variables will be summarized as medians and interquartile ranges (IQR) for non-normally distributed data.
 - Categorical variables will be expressed as percentages.
- Group Comparisons:

- Continuous variables: Mann–Whitney U test.
- Categorical variables: Pearson's χ^2 -test.

3.2 Survival Analysis

• Nonparametric Analysis:

- Kaplan–Meier survival curves will be generated for symptomatic and any HT, stratified by HT risk group and treatment arm. Log-rank tests will compare survival distributions.
- The proportional hazard (PH) assumption will be tested using graphical diagnostics and statistical methods, with alternative combined permutation tests if the assumption is violated.

• Semiparametric Analysis:

- Cox proportional hazards models will estimate hazard ratios (HRs) for symptomatic and any HT, adjusting for HTI category and treatment group.
- If the PH assumption is violated, time-dependent Cox models with time-varying covariates will be employed.

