3.3 Parametric Analysis and Model Selection

• Parametric Survival Models:

- Candidate models include Gompertz, Weibull, exponential, log-logistic, lognormal, and Royston–Parmar flexible parametric models. Model fit will be assessed using the Akaike Information Criterion (AIC), Bayesian Information Criterion (BIC), and Cox–Snell residual plots.
- The model providing the best fit will be used to estimate hazard rates, survival probabilities, and restricted mean survival times.

• Hazard Deceleration (HD) Analysis:

- HD curves will be derived from the parametric hazard function, capturing changes in hazard rates over time.
- Inception points for anticoagulation resumption will be identified based on HD values falling below 5% of the initial hazard peak, indicating stabilization of HT risk.

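### Time to any HT is modelled without an event-time definition or interval censoring, although imaging is scheduled only at days 1, 7 and 14, so hazard shape, deceleration and RMST depend on the scan schedule

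*SAP*

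**What the plan says.** Section I.6 gives the imaging schedule after baseline: "Day 1: Follow-up imaging and NIHSS assessment" and "Day 7 and Day 14: NIHSS score, follow-up CT, and DTI imaging on day 14".

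Section III is the survival analysis added in April 2024. Its introduction (III.1) states that "outcomes will be analyzed for both symptomatic and any HT within 14 days". The methods follow in III.3.2 and III.3.3:

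- Nonparametric: "Kaplan–Meier survival curves will be generated for symptomatic and any HT, stratified by HT risk group and treatment arm", with log-rank tests.
- Semiparametric: "Cox proportional hazards models will estimate hazard ratios (HRs) for symptomatic and any HT, adjusting for HTI category and treatment group".
- Parametric: "Candidate models include Gompertz, Weibull, exponential, log-logistic, lognormal, and Royston–Parmar flexible parametric models", chosen by AIC, BIC and Cox-Snell plots. The best-fitting model also supplies hazard rates, survival probabilities and RMST.
- Deceleration: "HD curves will be derived from the parametric hazard function, capturing changes in hazard rates over time". From these, "Inception points for anticoagulation resumption will be identified based on HD values falling below 5% of the initial hazard peak".

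Section III.2 makes the timing of anticoagulation resumption, defined by those inception points, a primary endpoint beside 14-day HT incidence. RMST differences are secondary. The SAP does not define the HT event time, say how an HT found on a scheduled scan is dated, or name an interval-censored or discrete-time method. The one sensitivity analysis in III.3.5 compares parametric with semiparametric models by a Hausman test.

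**The concern.** Any HT includes bleeding without symptoms, which only imaging reveals. On this schedule such an event is known to have occurred in (0,1], (1,7] or (7,14] days, and no more precisely unless an unscheduled scan happens to date it. If the listed methods are run in their usual right-censored form on detection dates, a bleed of day 2 first seen on the scheduled CT enters the analysis at day 7.

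That matters here because a primary endpoint of Section III rests entirely on how fast the hazard falls, and delayed dating damages that quantity directly. RMST is affected too, because event-free time is credited up to the scan. The Hausman comparison cannot reveal the problem: both models would use the same event times.

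**Working it through.** The SAP gives no sample size, event count, inception day or RMST value for Section III, so there is no stated figure to reproduce. The check is an illustration at population level (expected likelihood, no sampling error).

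**Inputs from the SAP.** Scans at days 1, 7 and 14 (I.6). Control HT risk 20% and target OR 0.5 (I.4). The odds are 0.20/0.80 × 0.5 = 0.125, so the risk with Cerebrolysin is 0.125/1.125 = 11.1%. The 5% threshold is from III.3.3.

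**Assumptions not in the SAP.** A Gompertz hazard h(t) = λe^(gt), with g = −0.2, −0.3, −0.5 or −1.0 per day; λ set so that the 14-day risk is 20% or 11.1%; and either all events dated at the next scan, or half dated exactly.

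**Formulas.**

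- Cumulative hazard H(t) = λ(e^(gt) − 1)/g, and F(t) = 1 − e^(−H(t)).
- Scan dates as exact: maximise Σ w[ln λ + gt − H(t)] − (1 − F(14))·H(14), where w is the probability of an event recorded at time t.
- Interval-censored: maximise Σ w·ln[S(L) − S(R)] + (1 − F(14))·ln S(14).
- Day the hazard reaches 5% of its peak: ln(20)/|g| = 2.996/|g|.
- Scan-dated 14-day RMST: 1 + 6(1 − F(1)) + 7(1 − F(7)).

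**One case in full (g = −0.3, control).** λ = 0.2231 × 0.3/(1 − e^(−4.2)) = 0.0680. The probabilities in the three intervals are 0.057, 0.123 and 0.020. The fit that takes scan dates as exact gives g = −0.046, so the 5% day moves from 2.996/0.3 = 10.0 to 64.6. The interval likelihood returns g = −0.300 and day 10.0. RMST is 11.79 days in truth and 1 + 6(0.943) + 7(0.820) = 12.40 on scan dates. With Cerebrolysin the values are 12.78 and 13.12. The difference therefore falls from 0.99 to 0.72 days, or 27%.

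**All cases (5% day for the control arm; RMST difference between arms, in days).**

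| True g | True 5% day | All by scan: fitted g | All by scan: 5% day | Half exact: 5% day | RMST diff: true | all by scan | half exact |
|---|---|---|---|---|---|---|---|
| −0.2 | 15.0 | about 0 | not reached | 36.4 | 0.91 | 0.63 | 0.77 |
| −0.3 | 10.0 | −0.05 | 64.6 | 19.7 | 0.99 | 0.72 | 0.86 |
| −0.5 | 6.0 | −0.14 | 21.9 | 11.4 | 1.08 | 0.84 | 0.96 |
| −1.0 | 3.0 | −0.29 | 10.4 | 6.4 | 1.16 | 0.98 | 1.07 |

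The RMST difference is 16-30% smaller with all events dated by scan and 8-15% smaller with half dated exactly. In every case the interval likelihood recovers the true g from the same three scans. Days beyond 14 are extrapolations: they mean that the rule is not met within follow-up.

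**Dependence on the schedule alone.** With true g = −0.3, adding a day-3 scan changes the fitted g from −0.046 to −0.141 and the 5% day from 64.6 to 21.3, with no change in the disease process.

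**Other reading of the 5% rule.** If the rate of change |g|h(t) is set against 5% of the initial hazard, the day is ln(|g|/0.05)/|g|. The true values for the four cases are 6.9, 6.0, 4.6 and 3.0. With all events dated by scan, the criterion is already met at time zero in the first two cases, because fitted |g| is below 0.05, and is met at 7.4 and 6.1 in the others. With half dated exactly the days are 6.1, 7.3, 6.3 and 4.8.

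**The case against.** The strongest reply is that the SAP nowhere says that scan dates are the event times. A reader might infer that from the schedule and the method list, but the document does not state it. Unscheduled scans and the dating of HT may be covered in the protocol, which is not at hand. Section III.3.3 lists distribution families, not likelihoods, and the same families can be fitted with interval censoring. All this stands. The point is therefore that the event time is undefined and no interval-censored method is named, not that the plan prescribes an error.

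A reader might also infer that every result in Section III is distorted. The document does not support that. If all patients are scanned to day 14, 14-day incidence, and ARR and NNT read at day 14, are unaffected, and Kaplan-Meier is correct at the scan days themselves. No distortion of the log-rank test or the Cox hazard ratio has been shown. Symptomatic HT may be dated close to onset if deterioration prompts a scan, although the SAP does not say so.

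The size is also open to challenge. Dating every event by scan is the extreme case, and the direction of the shift in the 5% day depends on how the rule is read. The interval-censored recovery assumes the true family and no sampling error, so it says nothing about precision in a pilot trial. Model selection by AIC or BIC was not simulated.

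Finally, Section III is a later secondary analysis whose limitations paragraph asks for caution and prospective validation, and the trial's original primary analysis is untouched. That lowers the stakes, but the paragraph attributes its caution to post hoc stratification and does not mention event dating.

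**Conclusion.** The concern holds in a bounded form. For any HT, fits that treat detection dates as exact make the hazard shape, its deceleration (hence the primary timing endpoint) and RMST depend partly on when scans were booked. Nothing in Section III prevents or would detect this.

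Under the assumed Gompertz hazard the fitted decline is much too slow in every scenario, and RMST differences are too small. With the rule read as hazard against 5% of its peak, the inception day moves later, to beyond day 14 in three of the four cases when all events are dated by scan and in two of four when half are dated exactly. With the rule read literally, as rate of change against peak hazard, the shift ranges from about 7 days earlier to about 3 days later. The dependence on the schedule is common to both readings; the direction is not.

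These sizes rest on the assumed hazard shape, the range of g and the share of events dated exactly, none of which the SAP gives. Nothing here bears on when anticoagulation should resume.

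**What to change.** Define the HT event time in Section III. For any HT, code each event as (last HT-free scan, first HT-positive scan]. Take hazard shape, hazard deceleration and RMST from interval-censored parametric or flexible parametric fits, shown with a Turnbull curve. Use exact times only for HT confirmed on a scan prompted by clinical deterioration. Keep the scan-date analysis as a sensitivity check, and state which reading of the 5% rule is meant.

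The cost is SAP wording and reprogramming. It also needs individual scan dates, and the SAP does not say whether these are on file. Confidence intervals will be wider. With only three scheduled intervals, the shape inside (1,7] will rest on the chosen model, and the report should say so.
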